7 BACKGROUND INFORMATION AND RATIONALE

7.1 Prostate cancer in the United Kingdom (UK)

Prostate cancer (PCa) is the most common cancer and the second most common cause of cancerrelated death in men in the UK. There are >52,000 new cases diagnosed, and >12,000 PCa deaths, each year on average in the UK, and the lifetime risk of being diagnosed with PCa is around 1 in 8 men (1). PCa incidence is increasing due to wider use of Prostate Specific Antigen (PSA) testing of asymptomatic men coupled with an ageing population. The NIHR HTA ProtecT randomised controlled trial (RCT), led by the applicants, assessed the value of a single round of PSA testing in over 111,000 men in nine UK centres in the community, and compared the effectiveness of radical treatment (prostatectomy or radiotherapy) versus active monitoring in 1,643 men diagnosed with clinically localised PCa. ProtecT demonstrated that radical treatment of PSA-detected PCa halved the risk of subsequent disease progression and metastasis at a 10-year median follow-up. Moreover, PCa-specific mortality was very low at this 10-year median follow-up, with or without radical treatment. The study also defined the adverse urinary, bowel, and sexual side effect profiles resulting from the radical treatment options (2,3). Hence, most patients with low-risk (i.e. Gleason Grade Group 1), and many patients with low-volume lower-end intermediate-risk (i.e. Gleason Grade Group 2), PSA-detected localised PCa are now recommended to consider pursuing an initial policy of Active Surveillance involving regular clinical examination, PSA measurement, repeat mpMRI imaging +/- repeat biopsies, with radical treatment offered if indicated (4).

Men with intermediate-risk PCa (Gleason Grade Group 2-3) requiring treatment are usually recommended to receive radical treatment with curative intent in the form of Radical Prostatectomy (RP), Radical Radiotherapy (RRT) or Low Dose-Rate Brachytherapy (LDR-B). Partial Ablation (PA) is an alternative approach that aims to reduce treatment side effects while retaining oncological benefit, but its effectiveness compared to radical treatment has not been rigorously evaluated in the context of an RCT. The aim of PA is to target and treat only the part of the gland harbouring clinically significant PCa, thus minimising the morbidity of PCa treatment by reducing the adverse radical treatment sequelae of erectile dysfunction and urinary incontinence following RP, or erectile dysfunction, bowel and urinary toxicity following RRT. Several PA techniques have been developed including High

Intensity Focused Ultrasound (HIFU), Vascular Targeted Photodynamic Therapy (VTP), cryotherapy, Radiofrequency Interstitial Tissue Ablation (RITA), laser photocoagulation and irreversible electroporation (IRE) (5). Having demonstrated the feasibility of randomising men with unilateral intermediate-risk PCa to a radical treatment option or PA in our PART Feasibility Study (6) (section 7.7), this is a full RCT of PA versus radical treatment, which will build on and complement the ProtecT study, and provide essential evidence to inform commissioning and clinical practice.

7.2 Diagnosis of prostate cancer – evolution of the diagnostic pathway

Until recently PCa did not rely consistently on imaging to detect disease and guide tissue sampling for histological confirmation. Conventional Magnetic Resonance Imaging (MRI) has been used but with accuracy ranging from 50-92% (7). More recently, multiparametric MRI (mpMRI) has demonstrated high levels of accuracy in detecting clinically-significant PCa (8,9) mpMRI has a high negative predictive value of 90-95% for lesions >0.5 ml in volume, accepted as constituting clinically significant disease (10,11), and this has now transformed clinical practice. The contemporary diagnostic pathway for PCa now involves PSA-testing followed by a pre-biopsy mpMRI, following recent evidence from the PROMIS and PRECISION RCTs (12,13). Incorporating pre-biopsy mpMRI into the PCa diagnostic pathway has demonstrable benefits in allowing targeted biopsies of visible lesions seen on imaging, leading to an improved detection rate of "clinically significant" PCa, particularly unilateral intermediate-risk tumours that might be suitable for PA.

7.3 Radical treatment options for localised prostate cancer

In 2017 approximately 78% of men diagnosed with PCa in England were under 75 years old (Office for National Statistics), and around 7,500 would have been suitable for potentially curative therapies. Conventional radical treatments for localised PCa (RP and RRT) appear to have similar oncological outcomes at a median of 10 years' follow-up (2). Low dose-rate brachytherapy [LDR-B] (placement of radioactive seeds directly in the prostate) is also a recognised standard-of-care option for some men with suitable intermediate-risk disease (NICE, 2021). Radical treatment has the potential for significant short, medium and long-term side effects such as erectile dysfunction following both RP and RRT, urinary incontinence following RP, and bowel and urinary dysfunction following RRT.

7.4 Alternative to conventional radical treatment: partial ablation

The National Institute for Health and Care Excellence (NICE) in the UK recommends that PA treatments should only be used with special arrangements for clinical governance, consent and audit or research (15,16)Click or tap here to enter text., but demand for PA in intermediate-risk PCa is expanding. The lack of RCT-based evidence means that NICE and similar bodies globally are unable to make robust recommendations, highlighting the urgent need for this RCT. It is imperative to investigate whether PA can offer comparable oncological outcomes to radical treatments, with fewer potential side effects.

The PART Feasibility Study (6), along with other recently published evidence, has demonstrated that the side effects (in terms of erectile dysfunction and urinary incontinence) following PA are low after short-term (median 12-24 months) follow-up (17,18). Only 5% of PA-treated men had significant residual cancer following PA (18).

The PART Feasibility Study also established that mpMRI followed by systematic +/- targeted biopsies is required prior to minimally invasive PA to assess whether the disease is amenable to PA and has demonstrated that men can be recruited to such an RCT without necessarily needing an extended or template biopsy protocol.

Several PA technologies have been described and are summarised in a HTA synthesis review (5). These include HIFU, cryotherapy (19,20), RITA, interstitial laser photocoagulation, VTP and IRE. Having demonstrated their ability to ablate prostate tissue safely, PA technologies are currently being introduced and taken up in clinical practice without robust evidence of their utility, cost-effectiveness or medium- or long-term functional and oncological outcomes (16,17). We used HIFU as the PA technique in the PART Feasibility Study but encountered some practical limitations regarding the use of HIFU as the sole PA modality: 1) it required expensive equipment available only in a minority of UK NHS Trusts and some private providers; 2) the equipment was not readily available, and its lease from the manufacturers incurred a large expense which could not be covered by the Clinical Commissioning Groups. However, following recent developments, some of these limitations have been overcome, and in addition we have now added IRE as a PA modality in this main PART trial. AngioDynamics Inc. have agreed to partner with the PART study team by providing IRE equipment (AngioDynamics, Inc., NanoKnife System, Latham, NY USA) and training to any recruiting centre that requests it. EDAP TMS have also agreed to partner with the PART study team by providing their HIFU equipment and training to any recruiting centre that requests it. In addition, any site offering HIFU using the Sonablate system may also treat patients within PART. This will allow these well-tested PA technologies to be utilised in the PA arm of the trial.

An essential consideration for a PA strategy to be successful in treating intermediate-risk PCa is the ability to image and map the disease accurately, and this is now possible through use of mpMRI, as recently demonstrated by the PROMIS and PRECISION trials (12,13). In this proposal, PART participants will have undergone, as part of routine care, a pre-biopsy mpMRI and subsequent transrectal ultrasound guided (TRUS) biopsies, local anaesthetic transperineal (LATP) biopsies or transperineal template mapping biopsies as necessary. Repeat imaging will be used to follow-up men in the PA arm after treatment. The PA modalities included in PART are described below.

7.5 High Intensity Focused Ultrasound (HIFU)

HIFU uses ultrasound energy focused by an acoustic lens to cause tissue damage as a result of thermal coagulative necrosis and acoustic cavitation. The procedure is performed using a transrectal approach and is generally performed under general anaesthesia as a day case procedure. A transrectal probe incorporating an ultrasound scanner and a HIFU treatment applicator is inserted. The probe emits a beam of ultrasound, which is focused to reach a high intensity in the target area. Absorption of the ultrasound energy creates an increase in temperature, which destroys tissue. A cooling balloon surrounding the probe protects the rectal mucosa from the high temperature. HIFU continues to be a treatment option listed by NICE guidelines in 2019 'requiring further evaluation', and a recent NICE draft recommendation (October 2022) continues to support the rationale of the PART study, by stating that although there is sufficient evidence of safety with HIFU, evidence of treatment efficacy is lacking, and further research is needed, in particular RCTs. Several reviews of HIFU treatment of PCa have been published, and a recent meta-analysis and systematic review concluded that prospective RCTs of partial-gland HIFU were needed (21–23).

7.6 Irreversible Electroporation (IRE)

Irreversible Electroporation (IRE) is an image-guided tissue ablation technology that induces cell death via short, strong pulsed electric fields. Due to its non-thermal nature, IRE preserves vessels, nerves and extracellular matrix, making it an effective treatment modality for prostate cancer. IRE was cleared by the US FDA in 2011 for the surgical ablation of soft tissue. As of late 2022, 1,626 men with prostate cancer treated with partial ablation using IRE have been reported in 22 published studies

(24,25), with a favourable oncological (26,27) and safety profile (28–30). Interest in the IRE technology for PCa is increasing in the UK amongst clinicians and patients, and a number of patients have recently been treated at UCL in London. IRE is UKCA marked in the UK.

7.7 The PART feasibility study

In the PART Feasibility Study, 41 participants were randomly allocated to surgery (RP) and 41 to HIFU (as the PA treatment modality) (6). Analyses were performed using data from 71 participants. Participant characteristics were similar at baseline. The return rate for clinical CRFs and PROMs were 95% and 91% respectively. HRQoL outcomes relating to urinary and sexual function were better in the PA group (6) compared with RP, but no significant differences were observed in overall HRQoL between the two groups. Analysis of EuroQoL EQ-5D-5L utility scores was limited by small numbers but highlighted potential health gains for patients receiving PA compared to RP, with evidence suggesting that HIFU is unlikely to result in a loss in health benefit relative to RP. Five SAEs were reported, two of which were SUSARs and were reported to the REC.

Although the PART Feasibility Study was not powered to assess effectiveness of HIFU treatment compared to RP, the HRQoL outcomes are concordant with previous observational studies, which suggested that over the short- to medium-term HRQoL outcomes are better in patients treated with PA than RP. An indication towards better HRQoL and utility with PA added to the clear need to undertake a full RCT to quantify the level of benefit, and to determine overall clinical and cost-effectiveness, hence the full PART study.

7.7.1 Recruitment in the PART feasibility study

Recruitment is often challenging because of difficulties in explaining and justifying the concepts inherent in the trial design (such as randomisation and uncertainty) to patients (31). The QuinteT Recruitment Intervention (QRI) methodology was first developed to address such problems encountered with recruitment to the ProtecT trial, and QRIs have since been successfully integrated within 30 RCTs (32). We included an integrated QRI in the PART Feasibility Study to understand the recruitment process in the clinical centres and gathered evidence about the origin of difficulties as they occurred (using standard and novel qualitative research methods), and then produced rapid plans to address the recruitment difficulties in close collaboration with the Chief Investigator (CI), Trial Management Group (TMG) and Clinical Trials Unit (CTU). This process enabled the research team to understand and then overcome recruitment challenges (33).

In the PART Feasibility Study, five centres opened to recruitment between January and November 2015. In total, 236 patients (out of 329 screened individuals) were identified as eligible to participate by 31st March 2017, and 82 patients agreed to be randomised by 4th May 2017. The QRI findings showed that there was strong support for PART among recruiters. However, many had not previously been involved in RCTs, and in the early part of the PART Feasibility Study they found it challenging to explain aspects of the study, with some holding preconceptions about which treatment was preferable for patients and therefore finding it difficult to maintain equipoise. This meant that some clinicians were not comfortable approaching all eligible patients, and when the study was discussed, biases were conveyed through the use of particular terminology, poorly balanced information and treatment recommendations. The issues identified are common within many RCTs (31). Following the identification of these recruitment issues, the QRI team developed tailored strategies to optimise recruitment, including group training, individual feedback and 'tips' documents. The recruitment rate increased from 15/75 eligible (20%) (January-November 2015) to 67/161 (42%) (December 2015 to March 2017), and recruitment was achieved in four centres (with a clear understanding as to why it was not possible in the one other centre).

PART_Protocol_V3.0_15May2024_Clean.docx Page **20** of **77**

A QRI is integrated into this definitive trial to continue to support recruitment (see section 10). This will build on the findings from the PART Feasibility Study and will aim to understand the recruitment process as it occurs in the clinical centres/sites, to quickly gather evidence about the origin of difficulties (using standard and novel qualitative research methods), and then to produce a plan to address the difficulties in close collaboration with trial staff.

8 OBJECTIVES AND OUTCOME MEASURES

8.1 Aim

The aim of the PART study is to determine whether partial ablation for unilateral intermediate-risk prostate cancer provides effective oncological outcomes compared with radical treatment, with the added benefits of reduced side effects, and an improved patient reported outcomes profile.

8.2 Primary objective and outcome measure

Objective	Outcome measure	Time point(s) of evaluation of this outcome measure (if applicable)
To determine whether partial ablation provides effective oncological outcomes compared with radical treatment	Primary treatment failure (as defined in section 8.5)	After a minimum of 3 years median follow-up post- randomisation, with at least 12 months post- randomisation follow-up of the last recruited participant
To determine whether partial ablation has a reduced side effect profile, and an improved patient-reported outcomes profile, compared with radical treatment	Health-Related Quality of Life (HRQoL) as measured by the Patient Oriented Prostate Utility Scale (PORPUS-P)	Baseline, 6wks post- treatment and 3mths, 6mths, 12mths post- randomisation, thereafter every 12 months until the end of the study.

8.3 Secondary objectives and outcome measures

Objective	Outcome measure	Time point(s) of evaluation of this outcome measure (if applicable)
1. To compare the effect on HRQoL of both treatment arms	HRQoL using standard, validated patient-reported outcome measures (PROMs) questionnaires: IPSS, EQ-5D-5L, EPIC and MAX- PC (Modified 18 item)	Baseline, 6wks post- treatment and 3mths, 6mths, 12mths post-randomisation, thereafter every 12 months until the end of the study.
2.To compare the effect on health care resource	Health care resource utilisation and cost-effectiveness in terms	Baseline, 3mths, 6mths, 12mths post-randomisation,

		· · · · · · · · · · · · · · · · · · ·
utilisation of both treatment arms	of cost per quality-adjusted life year (QALY)	thereafter every 12 months until the end of the study.
3.To compare the short and medium term serious adverse events related to treatments in both treatment arms	Short, medium and long-term serious adverse events related to treatments	Short term: 31 days Medium term: 3 years
4.To determine the proportion of patients needing repeat partial ablation treatment	Proportion of patients needing repeat PA treatment in the PA group	Documentation of the need for repeat PA treatment in the PA group – at 1 year post- treatment and 3 years post- treatment (for those that reach this time point in the study's lifetime)
5.To evaluate the accuracy of current mpMRI imaging and biopsy protocols in determining suitability of patients for PA	The proportion of prostatectomy patients who develop high-risk disease or bilateral intermediate disease	After histopathological evaluation (only in men who have had RP, including salvage RP)
6.To determine disease progression beyond the prostate, including local spread and development of metastases	Time to disease progression (including local and distal recurrence)	At a minimum 12 months post-randomisation follow-up of the last recruited participant, but will be longer for those recruited early in the study.
7.To determine medium-term disease-specific and overall mortality	Time to disease-specific and overall mortality	At a minimum 12 months post-randomisation follow-up of the last recruited participant, but will be longer for those recruited early in the study.

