16.1 Overview

Table 3 shows scheduled assessments including sampling requirements for the study. Following randomised PCa treatment (PA or radical whole treatment), only the timepoints where mpMRI and biopsies are taken require study-specific hospital/in-person visits. All other study assessments will either be undertaken during a routine clinic visit, or electronically/over the telephone.

Table 3: Schedule of assessments

	Day/Week (W)/Month (M) post- randomisaton	Screening, consent & eligibility		Treatment start***	Day 7	6W ±2 wks**	3M ±4 wks	6M ±4 wks	9M ±4 wks	12M ±4 wks	24M [#] ±8 wks	36M ±8 wks	Annually until trial ends
	Initial eligibility screen	Х											
	Consent for "Information Study"**	Х											
	QRI audio recordings of study discussions with potential participants	Х											
	Informed consent for main PART study		Х										
	Eligibility assessment		Х										
	PSA blood test		Х*			Х	Х	Х	Х	Х	Х	Х	Х
	Randomisation		Х										
	Baseline data collection/CRF completion		Х										
RADICAL	Choose radical treatment (RP, RRT o LDR-B)		Х										
TREATMENT ARM ONLY	Radical treatment			Х									
PARTIAL	Choose partial ablation modality (HIFU or IRE)		Х										
ABLATION	Partial ablation treatment			Х									
ARM ONLY	mpMRI ***				Х					Х		Х	
	Prostate biopsy ***									Х		Х	
	Repeat PA treatment				Repeat	PA upon	prostate	biopsy	showing	g intern	nediate	e-risk d	isease
	Outcome data collection/CRF completion by		Х	Х		Х	Х	Х	Х	Х	Х	Х	Х
	local research team			Saf	ety reporting	will conti	inue thro	oughout	in acco	rdance	with s	ection	18
	HRQoL questionnaires		x			Х	Х	Х		Х	Х	Х	Х
	Health care use questionnaire		х				Х	х		Х	Х	Х	х

*blood test for PSA will be performed to confirm eligibility if no PSA test has been taken in the previous 90 days. **OPTIONAL consent. #assessments will be performed annually to end of study. ***assessments are from start of treatment, all other follow-up time points are post-randomisation.

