16.3.1 Prostate Biopsy (partial ablation arm only)

Participants undergoing PA will have biopsies at the following approximate time-points: 12 months and 36 months after receiving treatment.

Additional biopsies may be performed as a result of rising PSA levels (at least 50% increase over 12 months) or where there is clinical concern. Such biopsies will be performed in accordance with usual care.

The results of the biopsies will be used to determine the need for repeated PA treatment or treatment failure. See section 16.4.

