17 SAMPLES FOR LABORATORY ANALYSIS

17.1 Overview of study-specific samples

Table 4 provides a summary of all samples required by this study protocol

Sample Type and test(s) to be undertaken	Time point (post-treatment)	Analysis by local Trust lab or other
Blood sample for PSA test for eligibility*	Screening/Baseline	PSA tests will be arranged by sites in accordance with usual care practice and analysed by as per usual NHS practice.
Blood sample for PSA test	6 weeks 3 months 6 months 9 months 12 months 24 months** 36 months**	PSA tests will be arranged by sites in accordance with usual care practice and analysed as per usual NHS practice.
Prostate biopsy (PA arm only)	12 months 36 months** Clinical concern	Analysed by local laboratory

*blood test for PSA will be performed to confirm eligibility if no PSA test has been taken in the previous 120 days.

**[#]24-month and 36-month follow-up of all 800 participants is subject to receipt of additional funding for longer-term follow-up, and may not be collected for all participants. Where the test is standard of care this will be performed as usual outside of the study.

The above samples will be taken and processed by laboratories in accordance with local site practice. This includes labelling of samples with standard patient identifiers. Results will be reported back in the usual way according to local practice and accessed by the site research team. Such samples will be stored, held, reported and subsequently destroyed in accordance with standard local laboratory practice. Where required, data will be recorded within the CRF.

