18.2 Definition of Serious Adverse Events

A serious adverse event (SAE) is any untoward medical occurrence that:

- Results in death
- Is life-threatening
- Requires inpatient hospitalisation or prolongation of existing hospitalisation
- Results in persistent or significant disability/incapacity
- Consists of a congenital anomaly or birth defect
- Is otherwise considered medically significant by the Investigator

PART_Protocol_V3.0_15May2024_Clean.docx Page **51** of **77**

Significant medical events are medical events that may jeopardise the participant and may require an intervention to prevent one of the outcomes listed above.

NOTE: The term "life-threatening" in the definition of "serious" refers to an event in which the participant was at risk of death at the time of the event; it does not refer to an event which hypothetically might have caused death if it were more severe.

Seriousness vs severity

A distinction is drawn between serious and severe AEs. Severity is a measure of intensity whereas seriousness is defined using the criteria above. Hence, a severe AE need not necessarily be serious.

18.3 Reporting of Serious Adverse Events (SAEs) from sites to the central study team

Only serious adverse events considered by the site investigator to be related (possibly, probably or definitely) to any of the study procedures and in the opinion of the Principal Investigator are considered unexpected for the study procedure will be collected in the study. Such events must be reported within 24 hours to the central study team using the SAE form within the REDCap study database. Refer to section 18.6 regarding expectedness assessment.

Treatment complications listed in section 18.4 should not be reported on a SAE form unless the complication is (in the opinion of the site investigator) considered more severe in nature than might be expected, or unexpected, for the particular intervention received. For participants undergoing IRE or HIFU treatment, the user manual for the devices should also be referred to when making an assessment of expectedness.

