18.4 Treatment complications

The following treatment-related complications will be collected on the 'Treatment Complications' case report form and should not be reported separately on a SAE form unless the complication is (in the opinion of the site investigator) considered **more severe in nature than might be expected, or unexpected, for the particular intervention** received by the participant:

Events occurring intraoperatively, during the immediate post-operative period, or in the first 31 days post-procedure:

- Thromboembolic disease (DVT/PE)
- Respiratory complications
- Myocardial infarction
- Cerebrovascular accident
- Urine leak post-procedure requiring intervention
- Significant blood loss requiring intervention with either >3 units blood transfusion or packing of the pelvis and/or other surgical/radiological intervention
- Rectal perforation
- Bowel injury

Events occurring at any time during follow-up period likely related to a study intervention:

- Development of a recto-urethral fistula
- Development of a urethro-cutaneous fistula

PART_Protocol_V3.0_15May2024_Clean.docx Page **52** of **77**

- Development of post-procedure urethral stricture disease requiring subsequent surgical intervention
- Development of osteomyelitis
- Ureteric injury

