18.6.2 Expectedness

The Principal Investigator (or delegated individual) is responsible for assessing all serious adverse events for reason for causality. Only serious adverse events considered by the site investigator to be related (possibly, probably or definitely) to any of the study procedures should be reported to the CI or nominated person (NP) in the CTU. Such events must be reported within 24 hours to the central study team using the SAE form within the REDCap study database.

Assessment of expectedness will be made by the CI or NP. An unexpected event is not expected for the study intervention and is not listed in the treatment complications below. If in doubt, the CI will raise queries with the treating medical practitioner.

Related SAEs, which are in the opinion of the nominated person are considered unexpected for the study procedure will be submitted to the REC within 15 days of the CI/CTU becoming aware of the event, using the HRA report of serious adverse event form.

All intervention/study procedure-related SAEs will be recorded and reported to the REC as part of the annual reports.

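### Secondary outcome 3 is worded to count only treatment-related serious adverse events, and the collection rules may miss serious complications of the follow-up biopsies that only the PA arm is scheduled to have

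*Protocol*

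**What the plan says.** **Outcome.** Protocol 8.3, secondary objective 3, compares serious adverse events (SAEs) between the arms. Its outcome measure is "Short, medium and long-term serious adverse events related to treatments". Tertiary outcome 1 in 8.4 is limited to treatments in the same way.

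**Biopsies.** Section 16.3.1 states: "Participants undergoing PA will have biopsies at the following approximate time-points: 12 months and 36 months after receiving treatment". The schedule in 16.1 and the sample table in 17.1 confine these biopsies to the PA arm. Section 16.1 also says that after treatment "only the timepoints where mpMRI and biopsies are taken require study-specific hospital/in-person visits". Under 16.3.1 and 16.4 the biopsy results decide on repeat PA and help to determine primary treatment failure.

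**Collection of harms.** Five sections set the scope:
- 9.2 collects treatment complications and unexpected SAEs related to the study intervention.
- 18.3 opens with "Only serious adverse events considered by the site investigator to be related (possibly, probably or definitely) to any of the study procedures", then adds that only those that, in the Principal Investigator's opinion, "are considered unexpected for the study procedure will be collected in the study".
- 18.4 says: "The following treatment-related complications will be collected on the 'Treatment Complications' case report form". No item on its list is a biopsy complication.
- 18.6.2 says that SAEs related "to any of the study procedures should be reported to the CI or nominated person (NP) in the CTU", with no expectedness condition at that step.
- 18.7 has all SAEs related to the intervention or to study procedures recorded and reported annually to the ethics committee.

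**The concern.** The scheduled biopsies belong to the PA strategy: they are how residual disease is found and how repeat ablation is triggered. The radical arm has no counterpart. If the harm outcome counts only what is attributed to treatments, the comparison includes the benefit of biopsy-guided control in the PA arm but not the serious harm that the biopsies may cause. Such events from scheduled biopsies can arise in one arm only, so an omission cannot cancel between arms.

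The collection rules raise a second problem. If an event was never recorded because it was thought expected for a biopsy, no later decision about what to tabulate can recover it without going back to the notes.

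**Working it through.** The protocol has no figure to reproduce on this point. The check is a comparison of texts, followed by an illustration of scale.

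**Step 1. Does the protocol treat a follow-up biopsy as a treatment or intervention?** It does not. The 16.1 schedule has separate rows for PA treatment and prostate biopsy. Section 16.8 lists withdrawal from the study intervention and withdrawal from follow-up biopsies as different choices. Section 16.1 attaches study-specific visits to the biopsies, which makes them study procedures. Read literally, a biopsy complication is outside outcome 3.

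**Step 2. Would a serious biopsy complication be collected?**

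| Section | Related to what | Expectedness condition | Serious biopsy event covered? |
|---|---|---|---|
| 9.2 | Study intervention | Unexpected only | No, on the wording |
| 18.3 | Any study procedure | Unexpected for the procedure, judged by the Principal Investigator | Only if judged unexpected |
| 18.4 | Treatment | None (fixed list) | No biopsy item |
| 18.6.2 | Any study procedure | None for reporting to the Chief Investigator or nominated person | Yes |
| 18.7 | Intervention or study procedure | None for recording | Yes |

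Sections 18.3 and 18.6.2 also differ on who judges expectedness and against what. In 18.3 the Principal Investigator judges it for the procedure concerned. In 18.6.2 the Chief Investigator or nominated person judges it against the study intervention and the list of treatment complications. A site following 18.3 could regard a recognised biopsy complication as expected and file no SAE form, and the 18.4 form has no place for it. A site following 18.6.2 would report the same event.

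**Step 3. Illustration of scale.**
- PA arm: 400 men (section 9). With the 10% total dropout of 19.2, 400 × 0.90 = 360.
- Scheduled biopsies counted: the 12-month biopsy only, so 360. The 36-month biopsy is left out of the main illustration because it depends on further funding (9.2, 17.1). It is also timed from treatment, which may start up to 12 months after randomisation (section 6).
- Serious complication rate per biopsy: not in the protocol. Assumed range 0.5% to 3%.
- Expected events = biopsies × rate.
  - 360 × 0.005 = 1.8
  - 360 × 0.01 = 3.6
  - 360 × 0.03 = 10.8
- Per 100 PA men with one biopsy each: 0.5, 1 and 3.
- Probability of at least one event at the lowest assumed rate: 1 − 0.995^360 = 0.835.
- Outer bound, with all 400 men having both biopsies at 3%: 400 × 2 × 0.03 = 24.
- Radical arm: no scheduled biopsies, so none from this source.

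**The case against.** The strongest reply is that the safety section is wider than the outcome wording. Sections 18.3, 18.6.2 and 18.7 all refer to study procedures, and 18.8 defines relatedness by reference to any research procedure. Nothing says that biopsy events will be dropped from the between-arm table, and which recorded SAEs are tabulated is commonly left to the analysis plan, which is not at hand. The missing biopsy item in 18.4 even helps in one respect: under 18.6.2, an event that is not on the list points towards being unexpected, and so towards the SAE form.

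Most of this stands. A reader might infer that serious biopsy complications are certainly lost. The protocol does not support that, because at least the unexpected ones have a route into the database. The reply does not change the outcome definition, however, which the protocol itself fixes, and it does not remove the conflict between 18.3 and 18.6.2.

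Two other strong readings fail. One is that the missing events would be a stated fraction of all PA serious events. The only SAE count in the protocol is the five in the feasibility study (7.7). That count is pooled over both arms of 41 and is not attributed to treatment, so it gives no base for a fraction. The other is that the trial's claim of fewer side effects is undermined. Objective 3 is a neutral comparison. The reduced-side-effect objective is co-primary, is measured by PORPUS-P and is not filtered by attribution.

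It is also fair to say that treatment-related harm is a legitimate outcome in itself. That is a reason to keep it as a breakdown. As the only harm total it leaves out a burden that the schedule creates in one arm. For-cause biopsies do not carry the argument, since they are not confined to PA by schedule; it rests on the scheduled ones. Some men will decline those (19.10), which lowers the count.

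**Conclusion.** The point holds in limited form. As worded, outcome 3 excludes serious complications of study biopsies that only PA participants are scheduled to have. The collection rules disagree with one another, so a complication judged expected for a biopsy may be captured on neither the SAE form nor the complications form. Any resulting bias affects this secondary harm comparison, and the tertiary one worded like it, and runs in favour of PA. Neither co-primary outcome is touched.

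The size is not known. The illustration of about 2 to 11 PA-arm events rests on an assumed rate of 0.5% to 3%, on 360 men each having the 12-month biopsy, and on none of the events being counted. The true omission would be smaller if sites follow 18.6.2 and the events are tabulated, and larger if many 36-month biopsies are done on study. The inconsistency in the text does not depend on these figures.

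**What to change.** 1. Define secondary outcome 3, and tertiary outcome 1 with it, as SAEs related to the allocated treatment or to any protocol follow-up procedure, including prostate biopsy, regardless of expectedness.
2. Add serious biopsy complications to the 18.4 form, with a field for the causative procedure.
3. Report the total by arm, with treatment-only events shown separately, so that the narrower comparison is kept.
4. Align 9.2, 18.3, 18.4 and 18.6.2 on one scope, one standard of expectedness and one person who judges it. Expectedness should govern expedited reporting, not whether an event is collected.

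The cost is a protocol and CRF amendment with the approvals required by 24.5, and some retrospective capture for men already biopsied. Biopsy data are already collected at 12 and 36 months (16.6), which limits the extra work. The PA harm total may look slightly less favourable. The change is best made while follow-up is running, since events never recorded may not be recoverable at analysis.
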